## **8.1.4 Subject Disposition and Study Drug Exposure**

### **8.1.4.1 Subject Disposition**

The number and percentage of subjects who are enrolled and received at least one dose of study drug, and the number of subjects who prematurely discontinued and the reason for premature discontinuation will be summarized. Premature discontinuation of study drug will be summarized, with frequencies and percentages overall and by reason for discontinuation for all subjects who received at least one dose of study drug. Subjects may have multiple reasons for prematurely discontinuing study drug, but will be counted no more than once for the total ("Any Reason").

### **8.1.4.2 Study Drug Exposure**

Extent of exposure to study drug will be summarized for all subjects who received at least one dose of open-label study drug in Study M13-538. The duration (days) of study drug treatment in both open-label treatment period and combined RCT (Study M13-550 or Study M13-537) plus open-label treatment period will be summarized with the mean, standard deviation, median and range.

## **8.1.5 Efficacy Analysis**

### **8.1.5.1 Efficacy Variables**

The efficacy endpoints of this study include the ACR20/50/70 response rates at Weeks 6, 12, 24, 36, 48, 60, 72, 84, 96 and every 24 weeks thereafter until the end of the study.

A subject will be considered an ACR20/50/70 responder if:

1. The counts for both SJC and TJC have reduced from Baseline by 20/50/70% or more; and
2. At least three of the five remaining ACR core set measures show reduction of 20/50/70% or more in baseline assessment:
  - Patient's Assessment of Pain (VAS),

- Patient's Global Assessment of Disease Activity,
- Physician's Global Assessment of Disease Activity,
- Patient's Assessment of Physical Function by Health Assessment Questionnaire – Disability Index (HAQ-DI),
- hsCRP.

Other efficacy endpoints of this study are:

- Individual components of ACR at every scheduled study visit (Weeks 6, 12, 24, 36, 48, 60, 72, 84, 96 and every 24 weeks thereafter until end of the study):
  - TJC
  - SJC
  - Patient's Global Assessment of Disease Activity
  - Physician's Global Assessment of Disease Activity
  - Patient's Assessment of Pain
  - hsCRP
  - Health Assessment Questionnaire Disability Index (HAQ-DI)
- Proportion of subjects achieving low disease activity (LDA) or clinical remission (CR) based on DAS28 [CRP] or CDAI criteria respectively at Weeks 6, 12, 24, 36, 48, 60, 72, 84, 96 and every 24 weeks thereafter until the end of the study.
- Proportion of subjects achieving CR at Weeks 6, 12, 24, 36, 48, 60, 72, 84, 96 and every 24 weeks thereafter until the end of the study.
- Change from Baseline in DAS28 [CRP] at Weeks 6, 12, 24, 36, 48, 72, 96 and every 24 weeks thereafter until the end of the study.
- Change from Baseline in CDAI at Weeks 6, 12, 24, 36, 48, 72, 96 and every 24 weeks thereafter until the end of the study.
- Change from Baseline in Patient Reported Outcomes at Weeks 6, 12, 24, 36, 48, 72, 96 and every 24 weeks thereafter until the end of the study:
  - FACIT – Fatigue Scale,

- Work Instability Scale for RA (RA-WIS),
- EuroQoL-5D (EQ-5D).

The proportion of subjects achieving Low Disease Activity (LDA) or Clinical Remission (CR), and the proportion of subjects achieving CR will be evaluated at Weeks 6, 12, 24, 36, 48, 60, 72, 84, 96 and every 24 weeks thereafter until the end of the study. The criteria will be based on DAS28 [CRP] or CDAI as follows:

	DAS28 [CRP]	CDAI
LDA	$2.6 \leq \text{to} < 3.2$	$2.8 < \text{to} \leq 10$
CR	$< 2.6$	$\leq 2.8$

DAS28 [CRP] score will be determined based on a continuous scale of combined measures of TJC, SJC, Patient's Global Assessment of Disease Activity (PtGA) (in mm), and hsCRP (in mg/L).

$$\text{DAS28 [CRP]} = 0.56 \sqrt{(\text{"TJC28"})} + 0.28 \sqrt{(\text{"SJC28"})} + 0.36 \ln(\text{CRP} + 1) + 0.014 \text{PtGA} + 0.96,$$

where  $\sqrt{\phantom{x}}$  is square root and  $\ln$  is natural log. A score  $> 5.1$  generally means high disease activity;  $2.6 \leq \text{DAS28 [CRP]} < 3.2$  generally means low disease activity (LDA);  $\text{DAS28 [CRP]} < 2.6$  is generally considered clinical remission (CR).

Clinical Disease Activity Index (CDAI) is a composite index (without CRP) for assessing disease activity. CDAI is based on the simple summation of the counts of SJC28 and TJC28 along with Patient's Global Assessment (VAS [0 – 10 cm]) (PtGA) and Physician's Global Assessment (VAS [0 – 10 cm]) (PhGA) for estimating disease activity.

$$\text{CDAI} = \text{TJC28} + \text{SJC28} + \text{PtGA} + \text{PhGA}.$$

$$\% \text{ Improvement in Joint Count from Baseline in RCT} = \frac{[(\text{Number of Swollen/Tender Joints at Day 1 of RCT} - \text{Number of Swollen/Tender Joints at Current Visit}) / \text{Number of Swollen/Tender Joints at Day 1 of RCT}] * 100}$$

In this study, the level of disease activity is interpreted as remission ( $CDAI \leq 2.8$ ), low ( $2.8 < CDAI \leq 10$ ), moderate ( $10 < CDAI \leq 22$ ), or high ( $CDAI > 22$ ).

#### **8.1.5.2 Efficacy Analysis**

The efficacy analyses will be conducted with the analysis set described in Section 8.1.1 and the observed cases (OC). The OC analysis will not impute values for missing evaluations, and thus a subject who does not have an evaluation on a scheduled visit will be excluded from the OC analysis for that visit.

Frequencies and relative frequencies (percentages) of ACR20/50/70 will be summarized with 95% confidence intervals at each post-baseline time point.

The proportion of subjects achieving Low Disease Activity (LDA) or Clinical Remission (CR), and the proportion of subjects achieving CR will be evaluated at Weeks 6, 12, 24, 36, 48, 60, 72, 84, 96 and every 24 weeks thereafter until the end of the study.

Frequencies and relative frequencies will be reported with 95% confidence intervals by visit, and will be summarized based on DAS28 [CRP] and CDAI criteria respectively.

For each of the change from baseline measurement, namely, TJC, SJC, Patient's Global Assessment of Disease Activity, Physician's Global Assessment of Disease Activity, Patient's Assessment of Pain (VAS), HAQ-DI, hsCRP, DAS28 [CRP] disease activity score, and CDAI, the mean, standard deviation, median, and range will be reported at each post-baseline time point. For Patient Reported Outcomes variables including change from baseline analyses of FACIT, RA-WIS, and EQ-5D, the mean, standard deviation, median and range will be summarized by visit. Confidence intervals at an overall level of 95% will be provided.

The impact of time between completion of RCT and roll-over to OLE will be explored.

#### **8.1.5.3 Multiple Comparisons**

Not applicable.

## **8.1.6 Safety Analysis**

### **8.1.6.1 General Considerations**

All subjects who receive at least one dose of upadacitinib in this OLE study will be included in the safety analysis. Incidence of adverse events, serious adverse events, premature discontinuation, and changes from Baseline in vital signs, physical examination results, and clinical laboratory values will be analyzed by visit. Treatment-emergent adverse events will be tabulated by system organ class and by MedDRA preferred term. Mean change from Baseline for laboratory and vital signs data will be summarized by visit. For analyses purposes, baseline for vital signs, physical examination results, and clinical laboratory results for subjects will be the data collected at the visit immediately prior to starting double-blind treatment. In an alternate assessment for summarizing the safety and laboratory data, baseline data will be assumed to be the data collected at the visit immediately prior to starting treatment with active upadacitinib.

Incidence of adverse events, changes in vital signs, physical examination results, and clinical laboratory values will be analyzed.

Treatment emergent adverse events will be tabulated by system organ class (SOC) and by the Medical Dictionary for Regulatory Activities (MedDRA) preferred term. Mean change from baseline for laboratory and vital signs data will be summarized by visit.

Missing safety data will not be imputed.

The impact of time between completion of RCT and roll-over to OLE will be explored.

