**Safety:**

All subjects who receive at least one dose of upadacitinib during the OLE period will be included in the safety analysis. Incidence of adverse events, serious adverse events, premature discontinuation, and changes from Baseline in vital signs, physical examination results and clinical laboratory values will be analyzed by visit. Treatment-emergent adverse events will be tabulated by system organ class and by MedDRA preferred term. Mean change from Baseline for laboratory and vital signs data will be summarized by visit. For analyses purposes, baseline for vital signs, physical examination results, and clinical laboratory results for subjects will be the data collected at the visit immediately prior to starting double-blind treatment.

In an alternate assessment for summarizing the safety and laboratory data, baseline data will be assumed to be the data collected at the visit immediately prior to starting treatment with active upadacitinib.

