7.0 Patient Disposition

The number of subjects treated, completed or discontinued in the open-label treatment period will be summarized by treatment group sequence (defined in Section 9.1) as well as overall for the Open-Label Treated Population. The number of subjects discontinuing

from the open-label treatment period will also be summarized with the reasons for discontinuation collected from CRF by the following categories:

- Adverse event
- Withdrew consent
- Lost to follow-up
- Lack of efficacy
- Subject non-compliance
- Requires alternative (or prohibited) therapy
- COVID-19 infection
- COVID-19 logistical restrictions
- Other

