10.0 Safety Analysis

10.1 General Considerations

Safety analyses will include reporting of adverse events, laboratory, and vital signs measurements in open-label treatment period only. Safety analyses will be carried out using the Open-Label Treated Population, which includes all subjects who received at least one dose of open-label study medication.

Long-term safety analyses include reporting of AE rate adjusted by cumulative exposure, mean change from baseline in laboratory parameters and vital sign variables, and frequency of potentially clinically significant laboratory and vital signs values.

The treatment-emergent adverse event (TEAE) rate per 100 patient-years of exposure will be presented by the exposure groups defined in Section 8.1, namely

1. Upadacitinib 6 mg BID/15 mg QD
2. Upadacitinib 12 mg BID/30 mg QD
3. Upadacitinib 6 mg BID/15 mg QD post down titration
4. Any upadacitinib

Listing of subjects with TEAEs by SOC and PT will be provided. Frequency tables and listings of subjects meeting criteria for potentially clinically significant vital sign values and for potentially clinically significant laboratory values will be provided by the exposure groups defined in Section 8.1.

Mean changes from baseline in all continuous laboratory parameters and vital signs variables at each visit will be summarized by the treatment group sequences defined in Section 9.1, namely

1. Upadacitinib never titrated (6 mg BID/15 mg QD),
2. Upadacitinib titrated up and not down (6 mg BID/15 mg QD to 12 mg BID/30 mg QD), and
3. Upadacitinib titrated up and down (6 mg BID/15 mg QD to 12 mg BID/30 mg QD and then back down to 6 mg BID/15 mg QD).

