10.2.1 Overview of Adverse Events Rates per 100 Patient-Years of Study Drug Exposure

The number and percentage of subjects experiencing TEAEs will be summarized for each exposure group in the open-label treated population for the following AE categories:

- All TEAEs
- Treatment-emergent serious adverse events (SAEs)
- Treatment-emergent severe adverse events
- TEAEs reasonably possibly related to study drug
- TEAEs of special interest
- TEAEs leading to discontinuation of study drug
- TEAE leading to death
- All death

For this calculation, 1 year will be considered to be 365.25 days. For each exposure group, the numerator of the overall rate will be the total number of TEAEs reported for

the event; that is, a subject can contribute more than one event to the numerator. For each treatment group, the denominator of the rates will be the total number of days exposed to study drug summed across all treated subjects divided by 365.25. Please refer to Section 8.1 for the calculation of study drug exposure. The AE rate per 100 patient-years of exposure will be calculated as $(\text{[numerator/denominator]}) * 100$. The number of AEs reported (numerator), the total number of years of study drug exposure (denominator), and the AE rate per 100 patient-years will be presented for each exposure group.

In the AE overview summary, any event with an unknown severity will be considered as severe and any AE with an unknown relationship will be considered as having "reasonable possibility" of being related to study drug.

Additional AEs may be considered for tabulation/summary based on recommendations from Clinical and Safety as deemed appropriate.

10.2.2 Adverse Events Rates per 100 Patient-Years of Study Drug Exposure by System Organ Class and Preferred Term

the TEAE rate per 100 patient-years of exposure will be tabulated by SOC and MedDRA PT for each exposure group in the open-label treated population. The SOCs will be presented in alphabetical order, and the PTs will be presented in alphabetical order within each SOC.

The following summaries of adverse events will be generated:

- All TEAEs
- Treatment-emergent serious adverse events (SAEs)
- Treatment-emergent severe adverse events
- TEAEs reasonably possibly related to study drug
- Frequent TEAEs (reported at ≥ 2 E/100PY in any exposure group)
- TEAEs leading to discontinuation of study drug
- TEAE leading to death

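### No planned safety summary shows whether event rates change with time on drug: the SAP pools adverse event rates over the whole open-label period and reports discontinuation by reason without timing, while protocol 8.1.6.1 calls for analysis by visit

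*Protocol*

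**What the plan says.** **Protocol.** The general safety statement in 8.1.6.1 covers the incidence of AEs and then "serious adverse events, premature discontinuation, and changes from Baseline in vital signs, physical examination results, and clinical laboratory values will be analyzed by visit". The synopsis has the same sentence under Statistical Methods, Safety. The detail sections do not carry it through: 8.1.6.2.1 lists overall frequencies and percentages by system organ class, preferred term, severity and relationship, and 8.1.4.1 summarizes discontinuation overall and by reason.

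**SAP, adverse events.** Section 10.1 announces that "Long-term safety analyses include reporting of AE rate adjusted by cumulative exposure" and that "The treatment-emergent adverse event (TEAE) rate per 100 patient-years of exposure will be presented by the exposure groups defined in Section 8.1". Those groups are 6 mg BID/15 mg QD, 12 mg BID/30 mg QD, 6 mg BID/15 mg QD after down-titration, and Any upadacitinib. In 10.2.1, "the denominator of the rates will be the total number of days exposed to study drug summed across all treated subjects divided by 365.25". In the numerator, "a subject can contribute more than one event to the numerator". Numbers and percentages of subjects are also given. Sections 10.2.2 to 10.2.5 use the same exposure groups, without a time split.

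**SAP, discontinuation.** In 7.0, "The number of subjects treated, completed or discontinued in the open-label treatment period will be summarized by treatment group sequence" and overall, with nine reason categories. Section 8.1 separately counts subjects exposed for at least 6, 12 and 18 months and at least 2, 2.5, 3, 4 and 5 years.

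**SAP, by visit.** Among safety outcomes, only mean laboratory and vital-sign changes are shown visit by visit (10.1, 10.3.2, 10.4.2).

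**The concern.** The primary objective names long-term safety, and protocol 3.1 calls this the first upadacitinib study with treatment beyond 24 weeks. The AEs of special interest (AESIs) include malignancy, major cardiovascular events and thromboembolism, which might emerge late, and infections, which might be most frequent early. For both kinds, readers will ask how the rate moves with time on drug.

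Total events over total exposure is a sufficient summary only if the rate is constant. Otherwise it is an average weighted by person-time, and attrition shifts that weight towards early exposure. The exposure groups do not replace a time split. The 12 mg BID/30 mg QD group and the down-titrated group start accruing time only after a dose change, so dose and time on drug are confounded.

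The timing and reasons of discontinuation matter as well, because later As Observed results come from the subjects who remain.

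**Working it through.** **No plan figure to reproduce.** Protocol 8.2 gives only an expected enrolment of up to 500, with no event rate or precision target for the main study.

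**Inputs.** From the documents: 494 enrolled and about 312 weeks of treatment (SAP 4.2); rate = 100 × events / (exposure days / 365.25) (SAP 10.2.1). Assumed, because the documents give neither: retention and all event rates.

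**Step 1: ceiling on exposure.** 312 × 7 / 365.25 = 5.98 years. With no dropout, 494 × 5.98 = 2,954 PY, and a 12-week interval holds at most 494 × 84 / 365.25 = 113.6 PY.

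**Step 2: can a pooled rate separate patterns over time?** With annual dropout d and k = -ln(1 - d), PY in the interval [a, b] = 494 × (e^(-ka) - e^(-kb)) / k. Relative yearly risks were 1, 1.4, 1.8, 2.2, 2.6, 3 (rising), the reverse (falling) or constant, each scaled to a pooled 2.00 per 100 PY.

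| Annual dropout | Total PY | PY, year 1 / year 6 | Rising, year 1 to 6 | Falling, year 1 to 6 | Pooled, every pattern |
|---|---|---|---|---|---|
| 5% | 2,544 | 482 / 365 | 1.03 to 3.10 | 2.91 to 0.97 | 2.00 |
| 10% | 2,192 | 469 / 271 | 1.07 to 3.20 | 2.82 to 0.94 | 2.00 |
| 20% | 1,631 | 443 / 142 | 1.15 to 3.44 | 2.66 to 0.89 | 2.00 |

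**Step 3: what a split would recover.** Let R be the share still on drug at Week 312, taken as 40% to 70%, with k = -ln(R) / 5.98. Total exposure is then about 1,930 to 2,480 PY. Years 0-2 hold 37-44% of it and years 4-6 hold 24-29%.

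Example, R = 50%: k = 0.116; PY in years 0-2, 2-4 and 4-6 = 882, 699 and 550, total 2,131.
- Malignancy at 0.5, 1.0 and 1.5 per 100 PY gives 4.4, 7.0 and 8.2 events. The pooled rate is 0.92, and 0.90-0.96 over the retention range.
- SAEs at 7, 10 and 13 per 100 PY give 61.7, 69.9 and 71.4 events. The pooled rate is 9.5 (range 9.4-9.8). The reverse pattern pools to 10.3-10.6.

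The 95% limits on a late-to-early ratio lie a factor exp(1.96 × sqrt(1/E_early + 1/E_late)) either side of it. At R = 50% this is exp(1.96 × sqrt(1/61.7 + 1/71.4)) = 1.41 for the rising SAE pattern and exp(1.96 × sqrt(1/4.4 + 1/8.2)) = 3.2 for malignancy. Over the retention range it is about 1.4-1.5 for SAEs in either direction and 3.0-3.4 for malignancy.

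Comparing Weeks 0-48 with all time after Week 192, and applying the early and late rates to those windows, gives about 1.5 for SAEs and 4.2-4.5 for malignancy, with only about two early malignancies.

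**Step 4: literal by-visit tables.** SAP Table 1 has 27 post-baseline windows. One event in a full 113.6 PY window is 0.9 per 100 PY, with exact Poisson 95% CI 0.02 to 4.9. Reporting by visit would be too sparse for uncommon events. Ten events in 450 PY, about a year of exposure, give 2.2 (1.1 to 4.1).

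**The case against.** **The protocol commitment is loose.** In 8.1.6.1 the by-visit phrase closes a long list. The same section later restates the incidence of AEs without it, and the detail sections have no time split. The SAP agrees with those sections. This stands: the protocol is internally inconsistent. It does not remove the statement, which also appears in the synopsis.

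**Nothing shows that an analysis was removed.** A reader might infer that the SAP dropped a planned by-visit AE analysis. SAP 11.0 compares SAP versions and does not record an earlier version containing one, so that inference is unsupported.

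**The SAP is fuller than a single rate and a single total.** There are four exposure groups plus subject percentages. Discontinuation is split by three sequences and nine reasons. For Any upadacitinib, the exposure categories in SAP 8.1 come close to a retention table, and the number observed at each visit is reported for efficacy and laboratory results. All this stands, so it would be wrong to say that retention is invisible. Timing by reason and event rates by period are still missing. The listings of SAEs, deaths and AEs leading to discontinuation (10.2.6) have no interval denominators.

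**Dilution by attrition is modest.** With equal exposure throughout, the rising SAE pattern would pool to about 10; attrition moves this only to 9.4-9.8. This stands. Most of the loss comes from averaging.

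**The setting is descriptive.** There are no hypothesis tests, and a Data Monitoring Committee reviews safety regularly (SAP 4.4). That bears on the priority of the point. Committee review does not put a time-specific rate in the study report.

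**Conclusion.** The point holds as a gap in the planned summaries. AE, SAE and AESI rates are pooled over the open-label period within exposure group, and discontinuation by reason has no timing, so no planned summary shows whether event rates change with time on drug. That a pooled rate can hide the pattern is arithmetic. The sizes above rest on assumed retention, assumed event rates and independent events, and are not evidence about this trial.

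A reader might go further and infer that the study itself cannot show a duration effect. The documents do not support that: SAP 10.2 works from AE onset dates, and protocol 5.4.1 requires attempts to establish the date of last dose, so the analysis can be run.

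The gain differs by event. A change in SAEs of the assumed size would be visible. For malignancy, even a true tripling would have limits of roughly 0.9-1.0 to 9-10 in two-year periods, so period rates for rare AESIs are descriptive only. Late-period rates also describe only those still on drug. The change should be made, but the pooled summaries are not invalid as averages.

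**What to change.** 1. **SAP 10.2.** Add event rates per 100 PY with 95% CIs by time since first open-label dose, using the events and person-years of each interval. Use a few wide intervals, for example yearly or two-yearly. Cover all treatment-emergent AEs, SAEs, AEs leading to discontinuation, deaths and AESIs, at least for Any upadacitinib. State the CI method; because repeat events count, a simple Poisson interval may be too narrow.
2. **SAP 7.0.** Add a Kaplan-Meier curve of time to premature discontinuation overall, and cumulative incidence by main reason, treating the other reasons as competing.
3. **Reconcile the texts.** Align the by-visit wording in protocol 8.1.6.1 and the synopsis with protocol 8.1.4.1 and 8.1.6.2.1 and with the SAP, or record the departure and its reason.

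**Cost.** SAP wording, a few tables and one or two figures, all from data already collected. The price is wide intervals for rare AESIs, and the text should say that these are descriptive.

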### **8.1.6.2 Analysis of Adverse Events**

#### **8.1.6.2.1 Treatment-Emergent Adverse Events**

Adverse events (AEs) will be coded using the Medical Dictionary for Regulatory Activities (MedDRA) dictionary. Treatment-emergent adverse events, defined as AEs that began or worsened in severity after initiation of open-label study drug upadacitinib in

this OLE study, will be tabulated by system organ class (SOC) and MedDRA preferred term.

Adverse events starting more than 30 days following discontinuation of study drug will not be included in summaries of treatment-emergent AEs. Adverse events starting more than 30 days following discontinuation of study drug will be summarized separately as post-treatment AEs.

When summarizing adverse events by relationship or severity, if a subject has an event with unknown severity or relationship then the subject will be counted in the severity/relationship categories of "unknown" even if the subject has a second occurrence of the same event with a severity/relationship present. The only exception is if the subject has a second occurrence of the same event with the most extreme severity (i.e., "severe") or a relationship category of "reasonable possibility." In this case, the subject will be counted under these most extreme severity/relationship categories.

The AEs of special interest (including but not limited to serious infection, opportunistic infection, herpes zoster, TB, gastrointestinal perforations, malignancies, MACE, renal dysfunction, anemia, increased CPK, drug-related hepatic disorders and thrombotic and embolic events) will be summarized.

Subjects reporting more than 1 AE for a given MedDRA preferred term will be counted only once for that term using the most severe incident in each study period. Subjects reporting more than 1 type of event within an SOC will be counted only once for that SOC.

Frequencies and percentages of subjects with treatment-emergent AEs will be summarized as follows:

- Any event
- By system organ class, and preferred term
- By system organ class, preferred term and maximum relationship

- By system organ class, preferred term and maximum severity
- Any event and by system organ class and preferred term for events resulting in death
- Any event and by system organ class and preferred term for events resulting in study drug discontinuation
- Any event and by system organ class and preferred term for serious events
- Any event and by system organ class and preferred term for adverse events with a relationship of "reasonable possibility"
- Any event and by system organ class and preferred term for adverse events of special interest

All AEs leading to premature discontinuation of study drug will be presented in listing format.

A listing of treatment-emergent AEs grouped by SOC and MedDRA preferred term with subject ID numbers will be generated.

The post-treatment AEs will be summarized in the same way as the treatment-emergent AEs described above.

